Appendix 1: Trial Screening, Entry, Randomization, Treatment and Monitoring Flow Diagram

Appendix 2: Data Collection Throughout the Study

Study Period	Data Collection
Screening	Age, gender Diagnosis and treatment 6 month bleeding/thrombosis history (including active bleeding) If ineligible: reason for ineligibility
Consent	If consent refused: reason for refusal
Enrollment	Malignancy diagnosis and treatment Lifetime bleeding/thrombosis history Transfusion history Anticoagulation plan (per managing physician) Weight, CBC, metabolic panel
Active management	Daily platelet count Platelet transfusion threshold (and reason for deviation if present) Transfusion data (product, number, response when available) Daily bleeding assessment VTE symptom assessment Anticoagulation management (missed or held doses)
30 Day Follow-up	Platelet count Current platelet threshold Current anticoagulation plan 30 day bleeding/thrombosis history

Appendix 3: World Health Organization Bleeding Scale

	Grade 1	Grade 2	Grade 3
Oral and nasal	
 ➤ Oropharyngeal bleeding – total duration of all episodes in previous 24 hours ≤ 30 minutes* ➤ Petechiae of oral mucosa ➤ Epistaxis – total duration of all episodes in previous 24 hours ≤ 30 minutes* 	
 ➤ Oropharyngeal bleeding – total duration of all episodes in previous 24 hours > 30 minutes* ➤ Epistaxis – total duration of all episodes in previous 24 hours > 30 minutes* 	
 ➤ Any bleeding requiring RBC transfusion over routine transfusion needs†
Skin, soft tissue, musculoskeletal	
 ➤ Petechiae of skin ➤ Purpura ≤ 1 inch diameter ➤ One or more spontaneous hematomas in the soft tissue or muscle > 1 inch 	
 ➤ Purpura > 1 inch diameter ➤ Spontaneous hematoma in deeper tissues ➤ Joint bleeding (confirmed by aspiration, imaging study or other accepted technique) 	
 ➤ Any bleeding requiring RBC transfusion over routine transfusion needs†
Gastrointestinal	
 ➤ Positive stool occult blood test‡ 	
 ➤ Melanotic stool ➤ Hematochezia – visible red blood mixed in stool, not requiring a transfusion ➤ Hematemesis – grossly visible blood in emesis or in nasogastric drainage tube (not related or secondary to swallowed blood) 	
 ➤ Any bleeding requiring RBC transfusion over routine transfusion needs†
Genitourinary	
 ➤ Any biochemical or microscopic Hb/RBCs without red urine‡ ➤ Abnormal vaginal bleeding (Unexpected bleeding out of normal cycle or bleeding heavier than normal or breakthrough bleeding (patient on hormonal therapy to prevent bleeding)) with spotting 	
 ➤ Gross/visible hematuria without need for transfusion ➤ Abnormal vaginal bleeding (Unexpected bleeding out of normal cycle or bleeding heavier than normal or breakthrough bleeding (patient on hormonal therapy to prevent bleeding)) more than spotting 	
 ➤ Any bleeding requiring RBC transfusion over routine transfusion needs†

Pulmonary		
 ➤ Hemoptysis – visible blood ➤ Blood in broncho-pulmonary lavage, or blood tinged sputum (excluding those with nose or oropharyngeal bleeding) 	
 ➤ Any bleeding requiring RBC transfusion over routine transfusion needs†
Body cavity		
 ➤ Visible blood in body cavity fluid (e.g. red cells apparent in fluid aspirate) short of criteria for Grade 3 or 4 	
 ➤ Grossly bloody body cavity fluids and organ dysfunction with symptoms, and/or need to intervene (e.g. to aspirate), and/or need for transfusion
Central nervous system		
 ➤ Retinal bleeding without visual impairment ➤ Lumbar puncture with blood (>5 RBC/μL in CSF on microscopic analysis and non-traumatic tap), no symptoms and no visible red color 	
 ➤ Lumbar puncture with visible red color in absence of symptoms, and non-traumatic tap
Invasive sites		
 ➤ Bleeding at invasive sites (venipuncture sites, intravenous lines or catheter exit sites): active oozing at site for a cumulative total of > 1 hour in the previous 24 hours 	
 ➤ Any bleeding requiring RBC transfusion over routine transfusion needs†
Hemodynamic instability			
 ➤ Any bleeding associated with moderate hemodynamic instability (hypotension; >30mmHg fall or >30% decrease in either systolic or diastolic blood pressure) and requiring RBC transfusion over routine transfusion needs†

Grade 4:

- Any bleeding associated with severe hemodynamic instability (hypotension; >50mmHg fall or >50% decrease in either systolic or diastolic blood pressure, with associated tachycardia (heart rate increase of \geq 20% for 20 minutes) and requiring RBC transfusion over routine transfusion needs
- Fatal bleeding from any source
- Retinal bleeding with visual impairment (Visual impairment is defined as a field deficit, and patients with suspected visual impairment require an ophthalmologic consult for documentation)
- CNS symptoms with non-traumatic bloody lumbar puncture
- CNS bleeding on imaging study with or without dysfunction

RBC indicates red blood cell; Hb, hemoglobin; CSF, cerebrospinal fluid; Hg, mercury; and CNS, central nervous system

* Count actual bleeding (i.e. "running out" or need for basin, Kleenex, towel, etc.) not minor bleeding

†Red cell transfusion must be specifically related to treatment of bleeding within 24 hours of onset of bleeding

‡Not assessed in PLADO

Appendix 4: Outpatient Bleeding Diary

Instructions for completing your Bleeding Assessment:

- Please complete this checklist in the morning on a daily basis.
- Please think about what has happened and changed over the past 24 hours.
- If you are concerned about any of your signs or symptoms, contact your doctor: _____
- If you have questions about completing this form, contact your study team: _____
- Call 911 for life threatening emergencies.

Who is filling out this form?		 Patient  Caregiver	 Patient  Caregiver	 Patient  Caregiver	 Patient  Caregiver	 Patient  Caregiver	 Patient  Caregiver	 Patient  Caregiver
Location	Did you notice any...	Each morning, answer questions for yesterday: Yes – No – Unsure For example, on Monday, tell us about Sunday						
		Monday	Tuesday	Wednesday	Thursday	Friday	Saturday	Sunday
Mouth	Bleeding from your gums, inside cheeks, roof of mouth, under tongue or lips?	Yes – more than 30 minutes	Yes – more than 30 minutes	Yes – more than 30 minutes	Yes – more than 30 minutes	Yes – more than 30 minutes	Yes – more than 30 minutes	Yes – more than 30 minutes
		Yes – less than 30 minutes	Yes – less than 30 minutes	Yes – less than 30 minutes	Yes – less than 30 minutes	Yes – less than 30 minutes	Yes – less than 30 minutes	Yes – less than 30 minutes
		No	No	No	No	No	No	No
		Unsure	Unsure	Unsure	Unsure	Unsure	Unsure	Unsure
	Blood blisters in or around your mouth?	Yes – more than 5	Yes – more than 5	Yes – more than 5	Yes – more than 5	Yes – more than 5	Yes – more than 5	Yes – more than 5
		Yes – less than 5	Yes – less than 5	Yes – less than 5	Yes – less than 5	Yes – less than 5	Yes – less than 5	Yes – less than 5
		No	No	No	No	No	No	No
		Unsure	Unsure	Unsure	Unsure	Unsure	Unsure	Unsure
Nose	Bleeding from the nose?	Yes – more than 30	Yes – more than 30	Yes – more than 30	Yes – more than 30	Yes – more than 30	Yes – more than 30	Yes – more than 30

		minutes Yes – less than 30 minutes No Unsure	minutes Yes – less than 30 minutes No Unsure	minutes Yes – less than 30 minutes No Unsure	minutes Yes – less than 30 minutes No Unsure	minutes Yes – less than 30 minutes No Unsure	minutes Yes – less than 30 minutes No Unsure	minutes Yes – less than 30 minutes No Unsure
Skin	Very small red or purple spots on your skin (petechiae, less than 1/8 inch (about the size of a pencil tip)	Yes No Unsure	Yes No Unsure	Yes No Unsure	Yes No Unsure	Yes No Unsure	Yes No Unsure	Yes No Unsure
	If you have these spots, is it new?	Yes No	Yes No	Yes No	Yes No	Yes No	Yes No	Yes No
	Bruising greater than 1 inch? 1 inch = 	Yes – 1-2 bruises Yes – many bruises No Unsure	Yes – 1-2 bruises Yes – many bruises No Unsure	Yes – 1-2 bruises Yes – many bruises No Unsure	Yes – 1-2 bruises Yes – many bruises No Unsure	Yes – 1-2 bruises Yes – many bruises No Unsure	Yes – 1-2 bruises Yes – many bruises No Unsure	Yes – 1-2 bruises Yes – many bruises No Unsure
	Is the bruise new?	Yes No	Yes No	Yes No	Yes No	Yes No	Yes No	Yes No
	If your bruise is not new, is it larger than yesterday?	Yes No	Yes No	Yes No	Yes No	Yes No	Yes No	Yes No
	If you have bruises, how big is the biggest one?	Less than an inch More than an inch	Less than an inch More than an inch	Less than an inch More than an inch	Less than an inch More than an inch	Less than an inch More than an inch	Less than an inch More than an inch	Less than an inch More than an inch

	tarry (sticky black)?	Yes – in the toilet, too No Unsure	Yes – in the toilet, too No Unsure	Yes – in the toilet, too No Unsure	Yes – in the toilet, too No Unsure	Yes – in the toilet, too No Unsure	Yes – in the toilet, too No Unsure	Yes – in the toilet, too No Unsure
Urine	Pink, red, bloody drops, clots?	Yes No Unsure	Yes No Unsure	Yes No Unsure	Yes No Unsure	Yes No Unsure	Yes No Unsure	Yes No Unsure
Vaginal  Skip if male	Vaginal bleeding, including your period?	Yes – spotting only Yes – flow requiring pads No Unsure	Yes – spotting only Yes – flow requiring pads No Unsure	Yes – spotting only Yes – flow requiring pads No Unsure	Yes – spotting only Yes – flow requiring pads No Unsure	Yes – spotting only Yes – flow requiring pads No Unsure	Yes – spotting only Yes – flow requiring pads No Unsure	Yes – spotting only Yes – flow requiring pads No Unsure
Cough	Are you coughing up blood?	Yes No Unsure	Yes No Unsure	Yes No Unsure	Yes No Unsure	Yes No Unsure	Yes No Unsure	Yes No Unsure
Other Bleeding Symptoms								
If yes, describe :								
Blood Transfusions								
Blood Transfusions	Red blood cells and/or platelet transfusions at a non-study site	Yes No Unsure	Yes No Unsure	Yes No Unsure	Yes No Unsure	Yes No Unsure	Yes No Unsure	Yes No Unsure

	If yes, where:							
--	-------------------	--	--	--	--	--	--	--

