2.4 Risks/Benefits

The primary risk of a decreased platelet transfusion threshold would be that of increased bleeding rates. Platelet-type, or bleeding due to defects of primary hemostasis, tends to be primarily mucocutaneous, including epistaxis, gum bleeding and menorrhagia,¹⁰ rather than into soft tissue, joints or body cavities as with disorders of secondary hemostasis (clotting factor deficiencies, including those induced by anticoagulation). Thrombocytopenic bleeding in the unanticoagulated population is largely low grade (WHO grade 2 or less) and rarely requires intervention beyond platelet transfusion.^{6,11}

Potential benefits of a decreased platelet transfusion threshold are numerous. Objective benefits to the individual patient might include decreased rates of transfusion-related complications, including transfusion reactions, infections, volume overload and alloimmunization. Subjective benefits of decreased transfusion frequency/requirement might include improved sense of well-being and quality of life, particularly for outpatients who may require fewer trips for medical care and benefit from increased time at home. Systemic benefits might include decreased overall cost of care and decreased drain on resources, of particular importance when blood products are in short supply.

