7.6 Transfusion Delays/Modifications

The transfusion threshold may be temporarily increased (for up to 72 hours) if a higher platelet count is required for safety in the setting of a procedure (including lumbar puncture and central

line placement). Transfusions according to the randomized threshold should resume once the procedure has been completed and bleeding risk has returned to baseline as determined by the proceduralist and/or the subject's primary provider.

Transfusion thresholds may also be temporarily increased for minor bleeding events which do not meet criteria for grade 3 or 4 bleeding but are bothersome to the patient (e.g. brief but recurrent episodes of epistaxis, vaginal bleeding). If benefit is achieved and the patient or provider feel an increased transfusion threshold is required beyond 72 hours, or if this occurs on three or more occasions during the study period, randomization will be broken and transfusions will be administered at the discretion of the managing provider(s). The new threshold will be noted and the patient will be followed for outcomes until the conclusion of a 30-day period from the date of randomization.

If post-transfusion thresholds are checked and patients are noted to be platelet refractory (defined as a $<5 \times 10^9/L$ increase in platelet count 30 minutes following a transfusion on ≥ 2 occasions) efforts should be made, according to institutional protocol and at the discretion of the provider, to optimize transfusion strategy, including the use of HLA-matched units, if necessary. If the subject remains refractory, despite all available interventions, and unable to achieve the targeted platelet threshold, the decision to continue or withhold anticoagulation will be made at the discretion of the primary provider and the patient will break randomization and be taken off protocol.

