8.2.3 Hemorrhagic events (WHO grade 2, 3 or 4)

Hemorrhagic events will be defined according to the WHO bleeding criteria (Appendix 3). Grade 3 events will be defined as events requiring packed red cell transfusions over and above the subject's routine transfusion needs. This will be determined based on the clinical judgment of an investigator.

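### The mouth, nose and vaginal items of the outpatient diary do not match the Grade 1/Grade 2 cut-points in Appendix 3, so outpatient Grade 2 bleeding can be misgraded

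*Combined protocol and SAP*

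**What the plan says.** Section 8.2.3 defines hemorrhagic events by the WHO criteria in Appendix 3. For mouth and nose bleeding, Appendix 3 puts the Grade 2 cut-point at "total duration of all episodes in previous 24 hours > 30 minutes"; 30 minutes or less is Grade 1. For vaginal bleeding it grades only abnormal bleeding, described as "Unexpected bleeding out of normal cycle or bleeding heavier than normal or breakthrough bleeding". Spotting is then Grade 1 and anything more is Grade 2.

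The outpatient diary (Appendix 4) is completed each morning for the previous day. Its mouth item asks about "Bleeding from your gums, inside cheeks, roof of mouth, under tongue or lips", and the answers are more than 30 minutes, less than 30 minutes, no, or unsure. The nose item has the same answers. The vaginal item asks about "Vaginal bleeding, including your period" and offers spotting, flow that needs pads, no, or unsure.

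Section 2.4 describes platelet-type bleeding as mainly "mucocutaneous, including epistaxis, gum bleeding and menorrhagia". Section 7.6 gives "brief but recurrent episodes of epistaxis, vaginal bleeding" as examples of minor bleeding that bothers the patient.

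Under section 8.1.3 the diary is reviewed at each visit and collected weekly, alongside targeted history, examination and chart review. Appendix 2 lists a daily bleeding assessment during active management. Section 8.1.2 sets outpatient visits at about weekly and at most 12 days apart. Nothing states how a diary answer becomes a Grade 1 or Grade 2, or who decides.

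**The concern.** The diary uses the same 30-minute figure as the grading scale but not the same quantity. The scale sums all episodes in a day; the diary leaves open whether the answer means one episode or the day's total. For vaginal bleeding, the scale first asks whether the bleeding is abnormal, and the diary never does. The two errors run in opposite directions: repeated short mucosal bleeds can be graded too low, and normal periods too high. Both concern kinds of bleeding that section 2.4 names as typical of a low platelet count.

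Grade 2 or greater bleeding is a secondary endpoint here and the planned primary outcome of the full trial (section 13.2, Sample Size and Power). Section 3.1.2 says the pilot should report outcomes as a definitive study would, so the fit between diary and grading scale is part of what the pilot is trying out.

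**Working it through.** **Step 1: the two appendices compared.**

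| Site | Appendix 3, Grade 1 / Grade 2 | Diary answers | Gap |
|---|---|---|---|
| Mouth, nose | Summed time over 24 hours, ≤ 30 / > 30 minutes | < 30 / > 30 minutes, for yesterday | No request to sum; exactly 30 minutes has no box |
| Vaginal | Abnormal only: spotting / more than spotting | Spotting / pad flow, periods included | No question on whether the bleeding is abnormal |

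Mouth and nose example: 3 × 15 = 45 minutes, above 30, so Grade 2. Each episode is 15 minutes, so a patient who reads the item per episode ticks the lower box (Grade 1). Vaginal example: a normal period with pad flow is not gradable under Appendix 3, but its diary entry is the same as that for a Grade 2 bleed. The stool rows are broken in the available text and were not assessed.

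**Step 2: the plan's own figure.** The only computed figure that rests on this endpoint is the full-trial power in section 13.2 (Sample Size and Power): 125 per arm, 40% in both arms, margin 0.16, one-sided 0.05, about 84%. With a normal approximation and unpooled variance:

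- SE = √(2 × 0.40 × 0.60 / 125) = 0.0620
- Power = Φ(0.16 / 0.0620 − 1.645) = 82.6%, close to the stated 84%
- At 60% in both arms and margin 0.24: 98.7%, against about 99% stated

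These figures assume correct grading and do not depend on the diary's wording.

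**Step 3: what misgrading could do (illustration only).** The documents give no misgrading rate, so the rates below are assumptions. They are taken as equal in both arms and uncorrected at review. Let true rates sit at the margin, 56% against 40%. If a fraction s of true Grade 2+ patients is captured, the observed rates are 0.56s and 0.40s, and the chance of wrongly declaring non-inferiority is Φ((0.16 − 0.16s)/SE − 1.645), with SE taken at the observed rates.

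| Grade 2+ patients missed | Observed rates | Difference | Chance of a false non-inferiority finding |
|---|---|---|---|
| 0% | 56.0% v 40.0% | 0.160 | 5.0% |
| 10% | 50.4% v 36.0% | 0.144 | 8.3% |
| 20% | 44.8% v 32.0% | 0.128 | 13.1% |
| 30% | 39.2% v 28.0% | 0.112 | 20.2% |

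The relative risk stays at 1.40 in every row; only the absolute difference shrinks. If instead 5% or 10% of patients without a Grade 2+ bleed are falsely counted, the chance becomes 6.5% or 8.2%. At 10% the difference falls to 0.144 and the relative risk to 1.31.

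**Step 4: normal periods and the event rate (illustration only).** Section 13.3 plans 5 women among 12. If a fraction q of women had a normal period with pad flow counted as Grade 2, a true 40% would read as 0.40 + 0.60 × (5/12) × q. That gives 42.5% at q = 10% and 52.5% at q = 50%. Taking 5/12 treats every planned woman as able to menstruate, so it is an upper bound.

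**The case against.** The diary is nowhere named as the grading instrument. It can be read as a prompt for staff, who also have history, examination and chart review, and Appendix 2's daily bleeding assessment is not restricted to inpatients. The form sets a one-day window and takes one answer per site per day, which many patients will read as the day's total. Including the period is defensible, because Appendix 3 counts heavier-than-normal bleeding and a form that left periods out would miss it. Bleeds that lead to a raised threshold under section 7.6 reach a provider anyway. The form covers outpatient days only, and the pilot's bleeding analysis is descriptive.

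Most of this stands. A reader might infer that the diary cannot grade these bleeds, or that it is the only daily outpatient record. The documents support neither, given the other sources. What remains is practical: visits may be 12 days apart, and minutes the form did not ask the patient to add up are hard to recover later. Appendix 2 does not say how the daily assessment is made for outpatients; it may be the diary itself.

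**Conclusion.** The mismatch is plain on the page and can misgrade outpatient Grade 2 bleeding. How often it would do so is unknown. The effect is limited to the descriptive Grade 2+ endpoint and to the event rate, which section 13.2 (Sample Size and Power) lists among the factors in judging feasibility. Enrolment, compliance and the stated power are untouched.

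Two stronger readings should be resisted. One is that the event rate passed to the full trial will be wrong. The 40% planning rate rests on historical data, the site table in section 8.1 uses eligibility and consent, and a misgraded bleed changes a patient's status only if that patient has no other Grade 2+ bleed. The other is that one misgraded patient in an arm of about 6 (1/6 = 16.7 points) exceeds the 16-point margin. Any single patient moves a small arm that far, and the margin belongs to a trial of 125 per arm, where one patient is 1/125 = 0.8 points. The error rates in the working rest on assumed misgrading and show direction, not a forecast. This is a worthwhile, inexpensive improvement to the measurement, not a flaw that undermines the pilot.

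**What to change.** - **Mouth and nose:** ask the patient to add up all episodes in the past 24 hours, and offer more than 30 minutes or 30 minutes or less.
- **Vaginal:** keep the period in the item. When bleeding is reported, add one follow-up: is it outside the usual cycle, heavier than usual, or breakthrough on hormonal therapy?
- **Grading:** state in section 8.2.3 that study staff assign the WHO grade from the diary together with visit history and chart, so that the patient's tick alone does not decide it.

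The cost is a diary revision with IRB approval and one extra tick-box on days with vaginal bleeding. No extra visits are needed. Staff grading involves judgement in an unblinded trial, so the rule should be written down before it is used.

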Appendix 5: Modified FACT-Th18 Questionnaire

Please circle or mark one number per line to indicate your response as it applies to the past 7 days.

		Not at all	A little bit	Some -what	Quite a bit	Very much
An5	I have energy	0	1	2	3	4
An7	I am able to do my usual activities	0	1	2	3	4
Th1	I bleed easily	0	1	2	3	4
Th2	I bruise easily	0	1	2	3	4
Th3	I worry about problems with bruising or bleeding	0	1	2	3	4
Th4	I worry about the possibility of serious bleeding	0	1	2	3	4
Th5	I am bothered by nosebleeds	0	1	2	3	4
Th6	I am bothered by bleeding in my gums or mouth	0	1	2	3	4
Th7	I am bothered by pinpoint bruising beneath my skin	0	1	2	3	4
Th8	I am bothered by blood in my urine or stool	0	1	2	3	4
Th9	I am inconvenienced by platelet transfusions	0	1	2	3	4
HI7	I feel fatigued	0	1	2	3	4
Th 10	I avoid or limit physical activity (because of concern with bleeding or bruising)	0	1	2	3	4
Th 11	I avoid or limit social activity (because of concern with bleeding or bruising)	0	1	2	3	4
Th	I am frustrated by not being able to do my usual activities	0	1	2	3	4
Th 13	I worry that my treatment will be delayed (because of low blood counts)	0	1	2	3	4
Th 14	I worry that my treatment dose will be reduced (because of low blood counts)	0	1	2	3	4
Th	For women only: I am bothered by vaginal bleeding	0	1	2	3	4

Appendix 6: Suggested Management of Grade 3/4 Hemorrhagic Events

Supportive care should be initiated for all grade 3/4 hemorrhagic events. This may include but not be limited to:

- Local control measures, including surgical interventions if indicated
- Platelet transfusion
- PRBC transfusion
- Cryoprecipitate in the event of low fibrinogen
- IV fluids prior to arrival of the above products for hemodynamic instability
- Anti-fibrinolytic agents (e.g. epsilon amino caproic acid or tranexamic acid)

The decision of whether or not to use more aggressive pro-hemostatic interventions (including anticoagulant-specific antidotes, where available) is based on a number of factors, including anticoagulant agent and half-life, time since last dose, renal function and location/severity of bleed. If reversal is deemed necessary by the managing provider, suggested approaches may be found at <https://depts.washington.edu/anticoag/home/sites/default/files/GUIDELINES%20FOR%20REVERSAL%20OF%20ANTICOAGULANTS%20February%202016.pdf>.
